### 7.3.3. 24-Hour Urine Sodium Excretion

24-hour urine sodium excretion at each visit, including change from baseline, will be summarized as continuous variables.

At baseline and EOT, correlation between 24-hour average SBP and 24-hour urine sodium excretion at each visit will be assessed visually by scatterplots and analytically by Pearson and Spearman coefficients.

At EOT, correlation between 24-hour average SBP change from baseline and 24-hour urine sodium excretion change from baseline will be assessed visually by scatterplots and analytically by Pearson and Spearman coefficients.

### 7.3.4. Participant Global Impression of Change (PGI-C)

Likert scale PGI-C responses will be aggregated as Improved (3 levels), No Change (1 level), or Worsened (3 levels).

Categorical variable summaries of PGI-C and aggregated classifications will be reported for each symptom. Treating each response level as a numeric variable (valued 1-7), a continuous variable summary will also be reported for each symptom.

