#### **8.2.4. Patient Global Impression of Severity**

The PGIs is a single-item 7-point Likert-type rating scale that is widely used in clinical studies to assess the severity of a condition. Using this scale, participants will be asked to rate the level of severity of each of the following: diaphoresis, nocturia, edema, and enuresis.

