#### **8.2.5. Patient Global Impression of Change**

The PGIC is a 7-point Likert-type scale that is widely used to evaluate efficacy in clinical studies by assessing a participant's impression of response to treatment. Using this scale, participants will be asked to rate their impression of change for each of the following: diaphoresis, nocturia, edema, and enuresis.

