### 7.3.5. Participant Global Impression of Severity (PGI-S)

Likert scale PGI-S responses will be aggregated as Improved (3 levels), No Change (1 level), or Worsened (3 levels).

Categorical variable summaries of PGI-S and aggregated classifications will be reported for each symptom. Treating each response level as a numeric variable (valued 1-7), continuous variable summaries at each visit, including change from baseline, will also be reported for each symptom.

---

 Bloomfield and Park, "Night time blood pressure dip". World J Cardiol 2015; 7:373-376.

Crosstabulations and the McNemar-Bowker test will be performed to describe change in PGI-S responses between time points.

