## 11. MODIFICATION HISTORY

Version	Date	Description
3.0	05 Dec 2024	
 
• Revisions to align with latest Protocol Amendments.
 
• Updated GMA signatory
 
• Corrected calculation of sleep diary NTST parameter
 
• Corrected reference for AE severity coding
 
• Removed comparison of PGI-S vs PGI-C
 
• Clarified presentation of Protocol Deviations
 
• Clarified O'Brien-Fleming and Pocock alpha levels as one-sided
 
• Clarified application of visit windows in table presentations
 
• Removed presentation of LS mean differences for subgroups
 

2.1	15 Feb 2024	
 
• Correction to modification history section.
 

2.0	13 Feb 2024	
 
• General updates to align with Protocol Amendment 2.
 
• Clerical and style updates.
 
• Revised fixed day/night windows to align with international guidance and added threshold for using fixed windows in analysis.
 
• Clarified IA procedure and provided GSD alpha levels.
 

1.0	05 Jul 2023	Initial version

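### SAP 7.3.4 does not separate PGI-C answers by whether the symptom was present at screening, so each Improved percentage mixes prevalence with response

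*SAP*

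**What the plan says.** Protocol 8.2.5 describes the PGI-C as a 7-point scale on which "participants will be asked to rate their impression of change for each of the following: diaphoresis, nocturia, edema, and enuresis". It attaches no condition about having the symptom. The schedules of activities place the PGI-C at the EOT (V7) and early discontinuation visits.

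SAP 7.3.4 counts three levels as Improved, one as No Change and three as Worsened, and then says: "Categorical variable summaries of PGI-C and aggregated classifications will be reported for each symptom". It adds: "Treating each response level as a numeric variable (valued 1-7), a continuous variable summary will also be reported for each symptom". It names no analysis set, denominator or baseline condition. SAP 4 makes the Completer Set the default for primary analyses of effectiveness endpoints. SAP 5.5 splits summary tables by narcolepsy subtype, and its optional subgroups do not include baseline symptom status.

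The baseline information exists. Under Protocol 8.2.4, "participants will be asked to rate the level of severity of each of the following: diaphoresis, nocturia, edema, and enuresis", and the schedules place the PGI-S at screening (V1), V7 and early discontinuation. SAP 7.3.5 plans, for the PGI-S alone, "continuous variable summaries at each visit, including change from baseline, will also be reported for each symptom", and then: "Crosstabulations and the McNemar-Bowker test will be performed to describe change in PGI-S responses between time points". Nothing visible in SAP 7.3.4 or 7.3.5 links the two scales. The modification history for version 3.0 lists "Removed comparison of PGI-S vs PGI-C", which fits the current text and is not itself an error.

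**The concern.** The visible eligibility criteria require narcolepsy and stable twice-nightly high-sodium oxybate. Criteria 6 and 7 are withheld, but the note in Protocol 5.1 shows that they concern blood pressure. None of the visible criteria requires any of the four symptoms. A participant who had no enuresis or edema before the switch still has to rate change in it, and the natural answer is No Change or some degree of worsening. Such answers enter both the percentages and the mean.

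SAP 2.1.3 sets an exploratory objective on the effect of switching on participant-reported change in conditions. If the four Improved percentages are set side by side, a rare symptom that responds well can look unaffected beside a common one that responds no better. The Worsened row likewise merges new onset with aggravation of an existing symptom. The study is meant to inform providers, patients and payers (Protocol 1.1, SAP 1), who may take these percentages at face value.

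**Working it through.** **No stated figure to reproduce.** The documents give no prevalence, expected Improved rate or power for the PGI-C. Only the denominator can be checked. A one-sample t-test (one-sided 0.025, difference 3.5, SD 8.0, 90% power; Protocol 9.5, SAP 3.3) gives n = 57 with power 0.901, which matches the plan. The normal approximation gives 54.9.

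**Formula.** Let p be the share with the symptom at screening and q the share of those who report improvement. Assume that people without the symptom do not answer Improved. Then

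Improved% (all) = p × q, which cannot exceed p.

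If 4 is taken as no change, and the symptomatic average an assumed 2.5,

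mean (all) = 2.5p + 4(1 − p) = 4 − 1.5p.

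**Same response, different prevalence.** Here N = 57 and q is about 50%. Both p and q are assumptions, counts are rounded to whole people, and intervals are Clopper-Pearson 95%.

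| p | With symptom | Improved, all | Improved, symptomatic (95% CI) | Mean, all |
|---|---|---|---|---|
| 10% | 6 | 3/57 = 5% | 3/6 = 50% (12-88) | 3.85 |
| 20% | 11 | 6/57 = 11% | 6/11 = 55% (23-83) | 3.7 |
| 40% | 23 | 12/57 = 21% | 12/23 = 52% (31-73) | 3.4 |
| 60% | 34 | 17/57 = 30% | 17/34 = 50% (32-68) | 3.1 |
| 80% | 46 | 23/57 = 40% | 23/46 = 50% (35-65) | 2.8 |

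At the maximum of 77 completers the pattern is the same: 4/77 = 5% against 4/8 = 50% (16-84) at p = 10%, and 31/77 = 40% against 31/62 = 50% (37-63) at p = 80%.

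**Same prevalence, different response.** At p = 40%, moving q from 30% to 70% moves the overall figure from 0.4 × 0.3 = 12% to 0.4 × 0.7 = 28%.

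**Which factor dominates?** Taking p and q as spread evenly over a range, prevalence's share of the variance of log(p × q) is:
- 80% for p 10-60% and q 30-70%
- 67% for p 10-80% and q 20-80%
- 21% for p 30-60% and q 20-80%
- 19% for p 40-60% and q 30-70%

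The answer turns on ranges that the documents do not supply.

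**The case against.** Four arguments deserve weight.

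- **The denominator is inferred from silence.** A reader might infer that PGI-C is tabulated over everyone. The documents do not establish that. The default is the Completer Set. The lead-in to SAP 7.3, SAP 2.2.3, Protocol 9.3.4 and the exploratory rows of the objectives tables are redacted, and SAP 5.1 places table specifications in a separate document. Any of these could name a subset. This stands as a limit: the point concerns the visible text only.
- **PGI-S already shows the baseline.** The planned crosstabulation shows how many start at each severity level and where they move. That goes a good part of the way, since a reader can set baseline severity beside PGI-C. It cannot show how participants who had the symptom answered the PGI-C, because the two are not linked by participant.
- **People without the symptom at screening might still report improvement.** Response wording, anchors and recall period are not given, and symptoms can come and go. So the cap at p is approximate. This is also why the group without the symptom should have its full distribution shown.
- **An all-participant table is a legitimate description.** It shows how the treated population rated change. In a single-arm study, making a subset chosen on a fluctuating baseline the main summary could favour apparent improvement. This stands: the case is for adding a table, not for demoting the existing one.

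**Conclusion.** The point holds as a limit on interpretation. On the visible text, each PGI-C Improved percentage and 1-7 mean mixes baseline prevalence with improvement among those affected, and the four symptoms cannot be compared on them. Under the stated assumption, an identical 50% response shows as about 5% at 10% prevalence and about 40% at 80%, with 57 completers.

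A reader might go further and infer that the percentage mainly reflects prevalence. The documents do not support that. The figure is a product, neither factor is given, and prevalence's share of the variation runs from 19% to 80% over plausible assumed ranges.

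The consequence is small. PGI-C lies outside the testing hierarchy (SAP 5.4), SAP 7.3.4 plans no test on it, and no decision rests on it. The primary analysis and alpha are untouched. This is a cheap improvement, not a defect that threatens the trial.

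**What to change.** In SAP 7.3.4:

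1. Define symptom present from the screening PGI-S anchors. The documents do not state which level means absent. SAP 7.3.5 also applies the Improved / No Change / Worsened grouping to the PGI-S, a severity scale, and that should be clarified first.
2. Keep the all-participant table and state its analysis set.
3. Beside it, for each symptom, add a PGI-C summary among participants with the symptom at screening, with n and counts next to the percentages.
4. For those without the symptom at screening, give the full response distribution, including the number who worsened.
5. Label the addition exploratory and descriptive. Note that selecting on a fluctuating baseline without a control group can favour apparent improvement.

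The cost is SAP wording and one further table split, using data already collected. The downside is imprecision for rare symptoms: 3 of 6 carries an interval of 12% to 88%. Showing n makes that visible.

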### 7.3.5. Participant Global Impression of Severity (PGI-S)

Likert scale PGI-S responses will be aggregated as Improved (3 levels), No Change (1 level), or Worsened (3 levels).

Categorical variable summaries of PGI-S and aggregated classifications will be reported for each symptom. Treating each response level as a numeric variable (valued 1-7), continuous variable summaries at each visit, including change from baseline, will also be reported for each symptom.

---

 Bloomfield and Park, "Night time blood pressure dip". World J Cardiol 2015; 7:373-376.

Crosstabulations and the McNemar-Bowker test will be performed to describe change in PGI-S responses between time points.

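### SAP 7.3.5 puts change labels (Improved / No Change / Worsened) on PGI-S severity levels, so the aggregated class does not show the direction of change

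*SAP*

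**What the plan says.** - Protocol 8.2.4 defines the instrument: "The PGIs is a single-item 7-point Likert-type rating scale that is widely used in clinical studies to assess the severity of a condition". On it, "participants will be asked to rate the level of severity of each of the following: diaphoresis, nocturia, edema, and enuresis".
- Protocol 8.2.5 gives the companion change scale, the PGI-C, on which "participants will be asked to rate their impression of change for each of the following: diaphoresis, nocturia, edema, and enuresis".
- The Schedule of Activities (Protocol Tables 3 and 4) places the PGI-S at Visit 1 (screening, on high-sodium oxybate), at the EOT Visit and at early discontinuation. It places the PGI-C only at EOT and early discontinuation.
- SAP 2.1.3 lists participant-reported change and participant-reported severity as two separate exploratory objectives.
- SAP 7.3.4 groups the change scale: "Likert scale PGI-C responses will be aggregated as Improved (3 levels), No Change (1 level), or Worsened (3 levels".
- SAP 7.3.5 groups the severity scale in the same way: "Likert scale PGI-S responses will be aggregated as Improved (3 levels), No Change (1 level), or Worsened (3 levels". It continues: "Categorical variable summaries of PGI-S and aggregated classifications will be reported for each symptom". With responses scored 1-7, "continuous variable summaries at each visit, including change from baseline, will also be reported for each symptom". It also plans cross-tabulations and a McNemar-Bowker test of PGI-S responses between time points.

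**The concern.** The Improved / No Change / Worsened grouping fits the PGI-C, because each PGI-C response is itself a statement about change. A PGI-S response describes a state on the day. A participant who reports a given severity of nocturia at EOT has not said whether it is better or worse than before. Only comparison with that participant's own baseline rating can show that.

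If a programmer follows SAP 7.3.5 literally, every aggregated PGI-S table, for all four symptoms, will show counts under headings that the data do not support. The study has one arm and no control, so no comparator column would expose the artefact. A percentage headed Improved would naturally be read as benefit from the switch.

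**Working it through.** **Inputs.** A seven-point PGI-S (Protocol 8.2.4). A grouping of 3 Improved, 1 No Change and 3 Worsened (SAP 7.3.5). A planned 57 to 77 completers (Protocol 9.5; SAP 3.3).

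**Step 1: what is being grouped?** The plan's split gives 3 + 1 + 3 = 7, which equals the number of raw response levels. If the grouping were meant for change from baseline, the difference on a 1-7 scale would run from -6 to +6. That is 13 values, split 6/1/6 by sign. The stated split fits raw levels and does not fit change.

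**Step 2: what holds under any 3/1/3 mapping?** The class is a function of the level at one visit, whereas direction needs two visits. Six of the seven levels carry the label Improved or Worsened, and each level has exactly one unchanged baseline-EOT pair. So 6 of the 7 unchanged pairs are labelled Improved or Worsened, whichever levels get which label.

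**Step 3: an illustration under an assumed coding.** Assume 1 = least severe, levels 1-3 = Improved, 4 = No Change, 5-7 = Worsened. The documents state neither the anchors nor the mapping. Compare the label at EOT with the true direction (lower than baseline = improved, equal = unchanged, higher = worsened) over all 7 × 7 = 49 pairs:

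| EOT level | Label | Pairs that disagree | Of these, opposite direction |
|---|---|---|---|
| 1 | Improved | 1 | 0 |
| 2 | Improved | 2 | 1 |
| 3 | Improved | 3 | 2 |
| 4 | No Change | 6 | 0 |
| 5 | Worsened | 3 | 2 |
| 6 | Worsened | 2 | 1 |
| 7 | Worsened | 1 | 0 |
| Total | | 18 of 49 | 6 |

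The 18 are made up of 6 pairs in the opposite direction, 6 unchanged pairs labelled Improved or Worsened, and 6 changed pairs labelled No Change. For example, 7 to 5 is an improvement labelled Worsened, and 1 to 3 is a worsening labelled Improved. If the numeric scale runs the other way (7 = least severe, 5-7 = Improved), the counts are the same by symmetry.

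Comparing the classes between visits does not restore the information. Of the 49 - 7 = 42 changed pairs, 12 stay within one class (3 × 2 within levels 1-3, plus 3 × 2 within levels 5-7).

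**Step 4: the McNemar-Bowker test.** SAP 7.3.5 does not say whether the test uses the seven levels or the three classes.
- Seven levels: 7 × 6 / 2 = 21 off-diagonal pairs. Even if every completer changed level, that is 57 / 21 = 2.7 to 77 / 21 = 3.7 participants per pair on average. Unchanged participants contribute nothing, so the table would be sparse.
- Three classes: 3 × 2 / 2 = 3 pairs. Sparseness is then much less of an issue, but the classes carry the wrong names.

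**The case against.** The strongest defence is that little depends on these tables. The PGI-S is exploratory and lies outside the four-endpoint SBP hierarchy of SAP 5.4, so its p-values are nominal. SAP 7.3.5 itself plans unaggregated categorical summaries, 1-7 summaries with change from baseline, and cross-tabulations. In a cross-tabulation of the seven levels, a participant whose symptom did not change sits on the diagonal. The PGI-C separately gives legitimate improved/worsened results for the same four symptoms. All of this stands and limits the harm, but it does not make the aggregated tables correct.

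Three stronger readings are tempting, and the documents do not support them:

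- *Mild symptoms at screening will be tabulated as Improved before any XYWAV.* No anchors are given, and nothing says which three levels count as Improved. In SAP 7.3.5 the visit-by-visit wording is attached only to the continuous summaries; the sentence on aggregated classes names no visit. Table specifications are in a separate document (SAP 5.1). Tabulation at baseline is a possible reading, not a stated plan.
- *The Bowker test has 21 discordant pairs.* That holds only for a 7 × 7 table. The SAP's other use of the test, for nocturnal dipping (7.3.2), is on three classes.
- *The PGI-S results as a whole are meaningless.* The unaggregated outputs show otherwise.

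The exploratory endpoint lists are redacted and may word the endpoint more fully. The rule in SAP 7.3.5 is legible, however, and is wrong as it stands.

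**Conclusion.** The point holds as a specification error in one paragraph. SAP 7.3.5 labels levels of severity as if they were statements of change, and its 3/1/3 split matches the raw scale and not the change from baseline. Under any mapping, the class does not show direction, and 6 of 7 unchanged pairs are called Improved or Worsened. The figure of 18 of 49 discordant pairs rests on the assumed coding. It counts possibilities and says nothing about how many participants would be misclassified.

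The effect is confined to the exploratory aggregated PGI-S tables and to any test run on those classes. No primary or secondary conclusion, alpha level, sample size or interim decision is affected. It should be corrected because the rule gives wrong tables if followed and is cheap to repair.

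**What to change.** Replace the aggregation sentence in SAP 7.3.5 so that:

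1. Improved / No Change / Worsened is derived per participant and per symptom from the sign of EOT minus baseline PGI-S, with no class assigned when either rating is missing.
2. Any collapsed bands reported per visit are named by severity, not by change.
3. The seven anchors, their numeric direction and any mapping to bands are stated.
4. The McNemar-Bowker test is tied to a named table: the seven levels, accepting sparseness, or the severity bands. A Wilcoxon signed-rank test of the paired difference is an optional alternative that uses the ordering.

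The raw categorical, 1-7 change and cross-tabulation summaries can stay. The cost is one SAP paragraph and a small change to the table shells, with no new data collection.

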**Table 6: Power and Sample Size Calculations**

Effect Size	Standard Deviation	80% Power	85% Power	90% Power
3.0	7.0	45	51	60
3.5	7.0	34	38	44
3.0	7.5	52	59	68
3.5	7.5	39	44	51
3.0	8.0	58	66	77
3.5	8.0	43	49	57

A preselected target sample size of 57 completers ( $n_0 = 57$ ) will provide 90% power to detect a difference of 3.5 points in means for the change from the baseline to the EOT Visit (after 6

weeks of treatment on XYWAV) in 24-hour average SBP when switching from twice-nightly high-sodium oxybate to XYWAV, assuming an SD of 8.0 points.

After 75% of participants have completed the study, an interim analysis will be conducted. If the study does not stop early for efficacy, conditional power for the primary endpoint will be calculated, and the adaptive sample size target may be increased up to a maximum of 77 participants (refer to Section [9.4](#)).

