### 3.3. Power and Sample Size Considerations

There are no historical data on 24-hour average BP changes in participants switching from high-sodium oxybate to XYWAV. Given the limited information, data from other studies with drugs similar to oxybate were leveraged to inform the design of this study. It was determined that an

effect size of 3.0 or 3.5 with a SD range from 7.0 to 8.0 will be considered for power and sample size calculations. Sample sizes for different scenarios (different effect sizes and SD) were calculated with a one-sided significance level of 0.025 (Table 2).

A preselected target sample size of 57 will provide 90% power to detect a mean 24-hour average SBP difference of 3.5 mm Hg between baseline and the EOT Visit after switching from high-sodium oxybate to XYWAV for 6 weeks, assuming an SD of 8.0 points.

This study will use a 2-stage group sequential design in which the final sample size may be adaptively determined. The primary endpoint will be evaluated at a planned interim analysis, with the option to terminate enrollment if the primary endpoint is met, or to adaptively modify the final study sample size if the primary endpoint is not met (see Section 3.5).

Assuming a 15% discontinuation/withdrawal rate during the Intervention Period, a minimum of 67 (up to approximately 91) participants will be recruited to initiate the switch to XYWAV and to capture complete data. Assuming a 60% screen failure rate during the Screening Period, a minimum of 170 (up to approximately 230) study participants will be enrolled (sign the ICF) into the study.

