### 3.5. Interim Analysis

The interim analysis will be performed after 43 participants (75%) have completed the study. Using the sample size assumptions described in Section 3.3, the calculated O'Brien-Fleming one-sided alpha levels for statistical significance are 0.00998 for the interim analysis and 0.02194 for the final analysis. If the primary endpoint is not rejected at the interim analysis, the final sample size will be adaptively determined based on conditional power.

Conditional power refers to the probability of reaching statistical significance at the final analysis given the data obtained at the interim analysis, and it is calculated according to equation (1):

$$CP = 1 - \Phi\left(\frac{z_{\alpha}\sqrt{n_2} - z_1\sqrt{n_1}}{\sqrt{\tilde{n}_2}} - \frac{z_1\sqrt{\tilde{n}_2}}{\sqrt{n_1}}\right) \quad (1)$$

Where:

$\Phi(\bullet)$  is the standard normal cumulative distribution function

$n_1$  = actual sample size at interim analysis (expected to be  $n_1 = 43$ )

$n_2$  = planned sample size at final analysis (i.e.,  $n_2 = 57$ )

$\tilde{n}_2$  = sample size increment between interim and planned final analyses (expected to be  $\tilde{n}_2 = 14$ )

$z_\alpha$  = the standard normal value for a type I error rate of  $\alpha$ ; i.e.  $\Phi(1-0.025)=1.95996$

$z_1 = \bar{x}_1 / se(\bar{x}_1)$ , the z-statistic for 24-hour SBP change from baseline computed at interim analysis

Given the conditional power, the final sample size target will then be determined using a "promising zone" approach:

- If  $CP \geq 90\%$  (Favorable zone): Continue enrolling more participants until prespecified target sample size ( $N = 57$ ).
- If  $CP < 40\%$  (Unfavorable zone): Continue enrolling more participants until prespecified target sample size ( $N = 57$ ).
- If  $40\% \leq CP < 90\%$  (Promising zone): Calculate additional sample size  $\tilde{n}'_2$  based on formula (2). The final sample size target will be adjusted to  $\min(77, n_1 + \tilde{n}'_2)$ .

$$\tilde{n}'_2 = \left( \frac{n_1}{z_1^2} \right) \left[ \frac{z_\alpha \sqrt{n_2} - z_1 \sqrt{n_1}}{\sqrt{n_2} - \sqrt{n_1}} + z_\beta \right]^2 \quad (2)$$

Where:

$n_1$  = actual sample size at interim analysis (expected to be  $n_1 = 43$ )

$n_2$  = planned sample size at final analysis (i.e.,  $n_2 = 57$ )

$z_\alpha$  = the standard normal value for a type I error rate of  $\alpha$ ; i.e.  $\Phi(1-0.025)=1.95996$

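### The only planned test of change in the 7-level PGI-S (McNemar-Bowker) ignores level order and, at 43 to 77 pairs, has little power for small to moderate shifts; a Wilcoxon signed-rank test would serve better

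*SAP*

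**What the plan says.** Protocol 8.2.4 describes the instrument: "The PGIs is a single-item 7-point Likert-type rating scale". It is rated separately for four symptoms: "participants will be asked to rate the level of severity of each of the following: diaphoresis, nocturia, edema, and enuresis". Protocol Tables 3 and 4 schedule it at screening, at the EOT Visit and at early discontinuation.

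SAP 7.3.5 names one inferential procedure for change: "Crosstabulations and the McNemar-Bowker test will be performed to describe change in PGI-S responses between time points". The same section scores the levels 1 to 7 and adds that "continuous variable summaries at each visit, including change from baseline, will also be reported for each symptom". Under SAP 5.1, a continuous summary is n, mean, SD, median, minimum and maximum; no confidence interval or test goes with it.

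SAP 7.3.5 also collapses the seven levels into three classes. It does not say outright whether the test uses the raw levels or the classes, nor how cell pairs with no observations are treated. SAP 5.4 makes everything outside the four-endpoint SBP hierarchy exploratory, with nominal p-values.

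On numbers, SAP 3.3 says "A preselected target sample size of 57 will provide 90% power to detect" the primary effect. SAP 3.5 says "The interim analysis will be performed after 43 participants (75%) have completed the study", and Protocol 9.5 says "the adaptive sample size target may be increased up to a maximum of 77 participants".

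**The concern.** McNemar-Bowker asks whether a square table is symmetric about its diagonal. It compares each off-diagonal cell with its mirror image and adds up the squared discrepancies, treating the levels as nominal. A drift of most participants towards lower severity is therefore split over many cell pairs, each judged on its own, instead of accumulating into one directional signal. With seven levels and a few dozen participants, many pairs hold only one or two people or none, and the chi-square approximation is poor.

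At stake is how the exploratory tables are read. Four nominal p-values, for diaphoresis, nocturia, edema and enuresis, would be the only inferential statements about change in PGI-S. If the test rarely rejects even when a moderate shift is present, a non-significant result carries little information but may be taken as evidence that severity did not change.

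**Working it through.** **Inputs from the documents.** Seven levels and four symptoms (Protocol 8.2.4). Completers: 57 as target (SAP 3.3), about 43 plus overruns if the study stops at the interim (SAP 3.5), at most 77 (Protocol 9.5).

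**The plan's own figure.** The sample sizes were "calculated with a one-sided significance level of 0.025". For 3.5 mm Hg and SD 8.0, the normal approximation gives ((1.95996 + 1.28155) × 8.0 / 3.5)² = 54.9, so 55. The one-sample t-test with the noncentral t distribution gives 57 (power 0.901), and all 18 cells of SAP Table 2 reproduce. That figure belongs to 24-hour SBP; the documents give no power or degrees of freedom for the PGI-S test.

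**Degrees of freedom.** k(k − 1)/2 = 7 × 6/2 = 21; the 5% critical value is 32.67.

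**A ceiling that needs no simulation.** The statistic is the sum over pairs of (n_ij − n_ji)² / (n_ij + n_ji). A pair holding m people contributes at most m, reached when all m move the same way. The statistic therefore cannot exceed the number of participants who change level. On 21 df, significance needs at least 33 changers: 33/43 = 77%, 33/57 = 58% or 33/77 = 43% of pairs.

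Example: of 57 participants, 32 improve, 25 are unchanged and none worsens. The statistic is 32 however the improvements are spread, and p = 0.059 on 21 df. A sign test gives p = 2 × 0.5³² ≈ 5 × 10⁻¹⁰. If empty pairs were not counted and every improvement were one level, at most 6 pairs would be occupied (critical value 12.59), and Bowker would reject clearly. The handling of empty pairs therefore matters.

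**Simulation.** Bivariate normal latent scores were cut into seven levels, with 1,500 trials per scenario and two-sided 0.05. Assumptions not in the documents: the baseline distribution (uniform, or skewed to low severity at 45/20/12/10/7/4/2%), the correlation, the shift and the alpha. Results for n = 57, correlation 0.5, as percent of trials rejecting:

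| Baseline | Latent shift (SD) | Mean change (levels) | Bowker, 21 df | Bowker, occupied pairs | Wilcoxon |
|---|---|---|---|---|---|
| Uniform | 0 | 0 | 0.1 | 0.9 | 5.8 |
| Uniform | 0.25 | 0.48 | 0.3 | 2.8 | 41.3 |
| Uniform | 0.5 | 0.94 | 3.5 | 15.5 | 91.9 |
| Uniform | 0.75 | 1.36 | 24.8 | 55.3 | 99.9 |
| Uniform | 1.0 | 1.74 | 69.0 | 92.8 | 100 |
| Skewed | 0 | 0 | 0.0 | 0.5 | 5.7 |
| Skewed | 0.25 | 0.34 | 0.0 | 3.3 | 31.5 |
| Skewed | 0.5 | 0.62 | 0.1 | 17.6 | 83.7 |
| Skewed | 0.75 | 0.83 | 0.7 | 57.5 | 98.5 |
| Skewed | 1.0 | 1.00 | 3.8 | 90.3 | 99.9 |

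Only about 10 to 18 of the 21 pairs are occupied on average, which is why the size falls so far below 5%. At correlation 0.7 and a 0.5 SD shift the figures are 4.8 / 32.6 / 98.7 (uniform) and 0.0 / 32.9 / 93.7 (skewed), in the column order of the table.

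Further simulation at correlation 0.6, n = 57, with uniform and skewed baselines, gives for shifts of 0.3-0.5 SD: 0-4% on 21 df, 4-24% on occupied pairs and 53-96% for Wilcoxon.

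**Other numbers of pairs, shift 0.5 SD.** n = 43 (correlation 0.6): 0-0.2%, 7-12% and 82-89%. n = 77 (correlation 0.5): 17.6 / 30.8 / 97.3 (uniform) and 1.3 / 31.7 / 93.5 (skewed).

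**The case against.** The case for leaving the text alone has real weight.

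- **Nothing rests on the test.** SAP 7.3.5 offers it as description, and SAP 5.4 makes its p-value nominal. This stands and keeps the point small.
- **The ordering is already used.** Numeric change from baseline is summarised for each symptom, and Protocol 8.2.5 asks directly about change in the same four symptoms. A reader might infer that the plan would report no change in the face of a clear shift. The documents do not support that: the mean and median change would show it, and a confidence interval can be worked out from n, mean and SD. What remains is that the only printed inference ignores the ordering.
- **21 df is a reading.** If the test were run on the three collapsed classes it would have 3 df, and simulated power at 0.5 SD and n = 57 would be 31-76%. The raw reading is more natural, because the section distinguishes PGI-S responses from aggregated classifications, and because the classes (improved, no change, worsened) do not describe severity at a single visit. Even 31-76% compares with 84-99% for Wilcoxon over the same scenarios.
- **Power is not poor for every shift.** A reader might infer that the test has almost no chance of finding any real change. That goes too far. At 1.0 SD and n = 57, power on 21 df runs from 4-8% (skewed) to 69-93% (uniform) over correlations of 0.5-0.7, and it is 33-79% in the simulation at correlation 0.6. Counting occupied pairs, it is 90-99%.
- **The replacement has limits.** Signed-rank treats steps between levels as comparable, drops participants with no change in its standard form, and tests directional shift, not table symmetry. These are modest costs here, since the SAP already scores the levels 1 to 7 and the interest is in whether severity shifted.

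**Conclusion.** The point holds as an inexpensive improvement to an exploratory analysis. If applied to the raw levels at 57 pairs, McNemar-Bowker has a size of about 0-1% and, for latent shifts of 0.3-0.5 SD, power of about 0-4% on 21 df or 4-24% on occupied pairs. A signed-rank test reaches about 53-96% while keeping close to its nominal size, so the difference is not bought with false positives. The gap is smaller for large shifts and at 77 pairs.

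The power figures rest on assumed baseline distributions, a correlation of 0.6 (0.5-0.7 widens the ranges somewhat) and two-sided 0.05. The number of pairs is approximate: the introduction to the exploratory analyses is redacted, so the PGI-S analysis set is not visible. The ceiling argument needs none of the distributional assumptions, only 21 df and a 5% level. No primary or secondary conclusion is affected.

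**What to change.** In SAP 7.3.5, replace the McNemar-Bowker test with a Wilcoxon signed-rank test on the change in PGI-S level (seven raw levels) from baseline to EOT, separately for each symptom, with nominal p-values. Preferably add a 95% confidence interval for the mean change. State how zero changes are handled. Keep the crosstabulation as description.

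Naming the raw levels also removes the doubt over which form of the responses is tested. The cost is one amended sentence and a small programming change, with no new data, since PGI-S is already collected at screening and EOT. The three-class use of McNemar-Bowker for nocturnal dipping in SAP 7.3.2 has only 3 df and does not need to change for this reason.
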